9.3 Sample Size Determination

The sample size determination for the Mini S Study and FORWARD PAD IDE pooled analysis is based on the Primary Safety Endpoint of MAE at 30 days and the Primary Effectiveness endpoint of Technical Success.

Primary Safety Hypothesis:

$$H_0: \Pi_S > PG_S \text{ vs. } H_A: \Pi_S \leq PG_S$$

where Π_S is the proportion of patients who experience an MAE within 30 days of the index procedure and PG_S is the Safety Performance Goal (PG).

The assumptions for the sample size calculations are listed below.

- Expected 30-day MAE rate of 2.0% = Π_S
- Performance Goal for 30-day MAE of 11.2% = PG_S
- One-sided statistical significance level of 0.025 = α
- The hypothesis will be tested using a one-sided Exact Binomial Test
- Statistical power of 96.5%

Primary Effectiveness Hypothesis:

$$H_0: \Pi_E \leq PG_E \text{ vs. } H_A: \Pi_E > PG_E$$

where Π_E is the proportion of patients with Technical Success and PG_E is the Effectiveness Performance Goal (PG).

The assumptions for the sample size calculations are listed below.

- Expected Technical Success rate of 97.0% = Π_E
- Performance Goal for Technical Success of 85.0% = PG_E
- One-sided statistical significance level of 0.025 = α
- The hypothesis will be tested using a one-sided Exact Binomial Test
- Statistical power of 98.1%

The performance goals are based on previous studies of peripheral IVL and benchmark plaque modification devices. Refer to the statistical analysis plan (SAP) for details.

A one-tailed scenario was used to assess the minimum sample size needed to detect a difference in the assumed true rate of safety (2%) versus the performance safety goal of 11.2%. The same calculation was done for the assumed true rate of effectiveness (97%) versus the performance effectiveness goal of 85%. The sample size of 90 subjects provides a study-wide power of 94.7% to meet both the safety and effectiveness endpoints. The study will be deemed a success if the null hypothesis is rejected for both the primary safety and effectiveness measures. No adjustments for multiplicity are needed.

 SHOCKWAVE <small>MEDICAL INC</small>	No.: CP 67398	REV. C
	TITLE: FORWARD PAD IDE Study Protocol	
	CLASS: CLINICAL PROTOCOL	PAGE 37 OF 65

9.4 Analysis Populations and Poolability

The primary analysis population for the FORWARD PAD IDE study will be the Intent-to-Treat (ITT) cohort which includes all enrolled subjects.

The FORWARD PAD IDE study is being conducted to supplement enrollment in the ongoing Mini S Study described in Section 3.1.3; data from subjects enrolled under the IDE protocol will be pooled with data from the Mini S Study to reach a total sample size of 90 subjects. Results for the first 90 consecutively enrolled subjects across both studies (with a minimum of 50% of subjects enrolled from in the US) will comprise the primary analysis cohort and will be submitted to support a Premarket Notification 510(k) application.

Justification of poolability is based on the following: The Mini S Study and the FORWARD PAD IDE Study protocols share the same eligibility criteria, data collection requirements and IVL treatment algorithm; both studies utilize the same electronic data capture system, are monitored with 100% source document verification, and include an independent angiographic core lab, independent clinical events committee (CEC) for endpoint adjudication of MAE and data safety monitor (DSM); and both studies use the XTR and FLX configurations of the JAVELIN catheter.

9.5 Handling of Dropouts or Missing Data

No imputation of or adjustments for missing data will be performed for the primary analyses. All available data will be presented. For time to event analyses, subjects who do not experience the event in question will be censored at their last known follow-up.

 SHOCKWAVE <small>MEDICAL INC</small>	No.: CP 67398	REV. C
	TITLE: FORWARD PAD IDE Study Protocol	
	CLASS: CLINICAL PROTOCOL	PAGE 38 OF 65

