5.1 Safety Endpoints

The safety endpoints for this study include:

- **PRIMARY: Major Adverse Events (MAE)** at 30 days defined as a composite of:
 - Cardiovascular death
 - Clinically-driven target lesion revascularization (CD-TLR)
 - Unplanned target limb major amputation (above the ankle)
- **MAE** at 6 and 12 months (as a composite and individual components)
- **Serious angiographic complications** defined as flow-limiting dissection (\geq grade D), perforation, distal embolization, or acute vessel closure as assessed by the angiographic core lab.

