APPENDIX A – DATA HANDLING AND ANALYSIS

This appendix provides additional details on the data handling and analysis of the study data.

Incomplete Data

If a date needed for calculation (e.g., date of birth for age) is an incomplete date (e.g., **112006 or ****2006) it will be completed as follows:

For incomplete event dates '01' or '0101' will be entered, respectively (worst case).

However, if an imputed event date is before the date of procedure, the date of event will be set equal to the date of procedure.

For all other incomplete dates '15' or '0107' will be entered, respectively (less far from correct date). If the missing month is known to be between July and December, the month September will be used.

If the entire start date of an event or a medication is missing, the procedure date will be imputed. Imputed dates will be limited to date of birth, AE start date, and medication start and end dates.

General Analysis Definitions

Assessments will be presented chronologically by study day, which is defined in the following:

Study day= assessment day – date of index-procedure.

Index-procedure day = 0. Events occurring on the day of the index-procedure will be considered day 0.

Events occurring on the day of discharge will be considered in-hospital.

Time of follow-up = date of last contact – date of index procedure. Where date of last contact is date of death or the latest of: date of last adverse event, date of last procedure, or date of last-follow-up visit.

Events will be reported as days elapsed since index procedure, or **Event Day** = event start date – index procedure date. Partial or missing dates will be imputed based on the rules described above. This approach avoids bias that increases with time since index procedure, as well as any confusion that may occur during event adjudication. For analysis at each time point, subjects will be censored at the time point or time to follow-up as defined above, whichever is earlier.

For all the clinical endpoints, the denominator will include subjects who either have an adjudicated event (e.g., death, revascularization) before the time of interest, or have a contact beyond the lower window of the follow-up.

Specific Reporting Conventions

Two types of endpoints will be reported – Clinical/safety endpoints and Core lab endpoints.

A. Clinical/Safety Endpoints

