Clinical endpoints include repeat revascularization procedures on target lesions/vessels, death, target limb amputations, and safety endpoints including Major Adverse Events, that occur within a specific time period. For each reporting period, the event rate will be defined as the number of subjects experiencing the event divided by the number of evaluable subjects. A subject will be considered evaluable for a reporting period if the study day of last contact is at or after the lower limit of the reporting window on the snapshot date. Acceptable study contacts include a study visit, adverse event, CEC adjudicated event date, image date, or other verifiable event that occurs during the active follow-up of a subject. Active follow-up ends when a subject completes the study, withdraws consent, or is considered lost to follow-up.

B. Core Lab Endpoints

Core lab endpoints include the endpoints that are determined by core lab assessment (duplex ultrasound or angiography), such as restenosis measured by duplex ultrasound or residual stenosis by angiography. Core lab endpoints rely on the actual evaluable assessment. If the scheduled assessment is not completed or the data are not evaluable (i.e., not readable or non-diagnostic), it will be treated as missing value and excluded from the analysis. Data will be used for subjects who have an evaluable (readable or diagnostic) scheduled duplex ultrasound.

C. Determination of Primary Patency Composite Effectiveness Endpoint

Primary patency contains both core lab endpoint (by visit) and clinical/safety endpoint (by cut-off days); the event of the individual component will be determined first, and the composite endpoint will then be determined.

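### The plan censors death without the event and names no single estimator for 6- and 12-month MAE, so two of the three available readings would modestly overstate the rates

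*Protocol*

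**What the plan says.** Three sets of statements bear on how MAE and its components will be estimated at 6 and 12 months.

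- **Censoring.** Protocol 9.5 and SAP 9.3 state that, in time-to-event analyses, "subjects who do not experience the event in question will be censored at their last known follow-up". SAP Appendix A (General Analysis Definitions) defines the end of follow-up: "Where date of last contact is date of death or the latest of" several contact dates. It adds: "For analysis at each time point, subjects will be censored at the time point or time to follow-up as defined above, whichever is earlier". A subject who dies without the event is thus censored on the day of death.
- **Crude rate.** SAP Appendix A, part A (Clinical/Safety Endpoints), says for each reporting period that "the event rate will be defined as the number of subjects experiencing the event divided by the number of evaluable subjects". On who counts: "A subject will be considered evaluable for a reporting period if the study day of last contact is at or after the lower limit" (meaning the start of that visit's window). General Analysis Definitions gives a second rule, under which "the denominator will include subjects who either have an adjudicated event (e.g., death, revascularization) before the time of interest", as well as those with a contact past the window's lower end.
- **Endpoint.** Protocol 5.1 and SAP 4.3 list MAE at 6 and 12 months, as a composite and by component. SAP 4.1 and most of the Protocol (2.0, 5.1, 15.1) count cardiovascular death only; Protocol 9.2.1 counts death from any cause.

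Neither document names Kaplan-Meier, cumulative incidence or a competing-risk method. SAP section 2 says that the SAP may modify and supersede the protocol's statistical plans.

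**The concern.** Censoring assumes that a censored subject could still have the event later, at the same rate as those still followed. That fails for a subject who has died. Any death makes CD-TLR and major amputation impossible. A non-cardiovascular death makes a later MAE impossible under the SAP definition. These are competing events. If they are censored, one minus Kaplan-Meier estimates the event probability in a hypothetical population without such deaths, which is higher than the proportion of subjects who actually have the event.

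The population includes Rutherford 5 and dialysis subjects (SAP 5.1), so some deaths within 12 months are plausible. What is at stake is the accuracy of the 6- and 12-month MAE, CD-TLR and amputation rates, and whether two analysts with the same data would report the same figure.

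**Working it through.** **The plan's own figures.** The documents give no expected rate for 6- or 12-month MAE or for mortality. Their figures concern the primary tests. With 90 subjects, a safety goal of 11.2% and one-sided alpha 0.025, the largest passing count is 4 MAEs: P(X ≤ 4 | 0.112) = 0.0218, whereas P(X ≤ 5 | 0.112) = 0.0537. Power at 2.0% is 0.9652. For effectiveness, at least 84 of 90 must succeed (alpha 0.0131), and power at 97% is 0.9812. The product is 0.9471. These match the stated 96.5%, 98.1% and 94.7%. They come from exact binomial tests on counts; no censoring rule enters.

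**Inputs for the check (assumed).** F1 is the true proportion with the event by the time point, 5-20%. F2 is the proportion who die of a competing cause without having had the event, 2-10%. Cause-specific hazards are constant.

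**Three readings of the plan.**

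1. One minus Kaplan-Meier with deaths censored: h1 = −ln(1 − F1 − F2) × F1/(F1 + F2); estimate = 1 − exp(−h1).
2. Crude rate, event-free early deaths dropped as not evaluable: F1/(1 − F2). This takes all competing deaths to fall before the lower window limit (day 360 − 30 = 330 at 12 months) and keeps subjects with the event in the denominator.
3. Crude rate, deaths kept in the denominator: F1.

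Aalen-Johansen cumulative incidence also returns F1.

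Worked example, F1 = 20%, F2 = 10%: −ln(0.70) = 0.3567; h1 = 0.3567 × 20/30 = 0.2378; 1 − exp(−0.2378) = 21.16%. Dropping deaths: 0.20/0.90 = 22.22%.

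| F1 | F2 | 1 − Kaplan-Meier | Deaths dropped | Deaths kept |
|---|---|---|---|---|
| 5% | 2% | 5.05% | 5.10% | 5% |
| 5% | 5% | 5.13% | 5.26% | 5% |
| 10% | 5% | 10.27% | 10.53% | 10% |
| 10% | 10% | 10.56% | 11.11% | 10% |
| 20% | 5% | 20.56% | 21.05% | 20% |
| 20% | 10% | 21.16% | 22.22% | 20% |

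The overstatement is about 0.05 to 1.2 points with Kaplan-Meier and about 0.1 to 2.2 points with deaths dropped. In counts: with 9 events and 5 competing deaths among 90 subjects, the crude rate is 9/90 = 10.0% or 9/85 = 10.6%.

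**Against sampling error.** The standard error √(p(1 − p)/90) is 2.3 points at 5%, 3.2 at 10% and 4.2 at 20%. In every row the bias is smaller than the standard error at that F1.

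**The case against.** The strongest reply is that the plan does not prescribe Kaplan-Meier. The censoring sentence applies only to time-to-event analyses and assigns no endpoint to them. Appendix A, part A, covers exactly these endpoints and defines a crude proportion, and the SAP may supersede the Protocol. A reader might infer from the censoring rule alone that the 6- and 12-month rates will be overstated. The documents do not support that: the overstatement depends on which estimator is used.

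This stands, but it does not remove the problem. Read as written, part A makes a subject who dies event-free before the window not evaluable, which inflates the rate by more than Kaplan-Meier does. Only the other Appendix A sentence, which gives death as an example of an adjudicated event that keeps a subject in the denominator, avoids the bias, and it conflicts with part A. Nor does any text exclude these endpoints from time-to-event analysis; Appendix A attaches censoring to the analysis at each time point.

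Other limits also stand:

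- On the all-cause wording of Protocol 9.2.1, no death competes with the composite, although deaths still compete with CD-TLR and amputation.
- Protocol 15.1 classes a death as cardiac when a cardiac cause cannot be excluded, which leaves fewer competing deaths.
- Inclusion requires a life expectancy above one year and Rutherford 6 is excluded, so high mortality should not be presumed.

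**Conclusion.** The point holds in conditional form. The plan treats death without the event as a censoring time, specifies no competing-risk method, and does not settle on one estimator or one denominator for MAE and its components at 6 and 12 months. Two of the three available readings bias the rates upward, by at most about 1.2 points (Kaplan-Meier) or 2.2 points (deaths dropped) over the assumed ranges; the third does not.

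The importance is low. The bias is below sampling error at 90 subjects, counts against the device, and affects secondary endpoints without a performance goal. The 30-day exact test does not use the time-to-event rule. All event and mortality rates in the check are assumptions.

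Two further inferences should not be drawn. Comparisons of below- with above-the-knee lesions are not shown to be distorted, because SAP 10.1 plans subgroup analyses for the primary endpoints only. Nor are these rates the only longer-term safety results, because Protocol 10.4 collects adverse events through 12 months.

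**What to change.** Amend Protocol 9.5, SAP 9.3 and both places in SAP Appendix A (General Analysis Definitions and part A) together; changing only the censoring sentence would leave the crude-rate definition in force beside it.

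- Name one estimator for MAE and its components at 6 and 12 months: Aalen-Johansen cumulative incidence with 95% confidence intervals.
- Treat non-cardiovascular death as competing for the composite and for cardiovascular death, and death from any cause as competing for CD-TLR and major amputation.
- Censor only living subjects, at last contact.
- If a crude rate is also shown, keep subjects who died in the denominator, and reconcile the two Appendix A denominator rules accordingly.
- Reconcile all-cause death in Protocol 9.2.1 with cardiovascular death in SAP 4.1, since this decides which deaths compete with the composite.

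The cost is wording and a standard SAS option; the data needed are already collected. The main figure would be slightly less comparable with published Kaplan-Meier rates, so Kaplan-Meier may stay as a supportive display.

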10.0 SAFETY EVENTS

Standard definitions and reporting requirements for reportable adverse events for the study are provided below. All adverse events will be coded using MedDRA.

Note: For any of the Adverse Event Definitions listed below, diagnosis should be reported versus individual symptoms leading to diagnosis.

10.1 Adverse Event Definitions

10.1.1 Adverse Event (AE)

Untoward medical occurrence, unintended disease or injury, or untoward clinical signs (including abnormal laboratory findings) in subjects, users or other persons, whether or not related to the investigational medical device and whether anticipated or unanticipated.

Note: This definition includes events related to the investigational medical device or the comparator.

Note: This definition includes events related to the procedures involved.

Note: For users or other persons, this definition is restricted to events related to the use of investigational medical devices or comparators.

10.1.2 Serious Adverse Event (SAE)

Adverse event that led to any of the following

- a) death,
- b) serious deterioration in the health of the subject, users, or other persons as defined by one or more of the following:
 - 1) a life-threatening illness or injury, or
 - 2) a permanent impairment of a body structure or a body function including chronic diseases, or
 - 3) in-patient or prolonged hospitalization, or
 - 4) medical or surgical intervention to prevent life-threatening illness or injury, or permanent impairment to a body structure or a body function,
- c) fetal distress, fetal death, a congenital abnormality, or birth defect including physical or mental impairment.

Note: Planned hospitalization for a pre-existing condition, or a procedure required by the CIP, without serious deterioration in health, is not considered a serious adverse event.

 SHOCKWAVE <small>MEDICAL INC</small>	No.: CP 67398	REV. C
	TITLE: FORWARD PAD IDE Study Protocol	
	CLASS: CLINICAL PROTOCOL	PAGE 39 OF 65

10.1.3 Adverse Device Effect (ADE)

Adverse event related to the use of an investigational device.

Note: This definition includes adverse events resulting from insufficient or inadequate instructions for use, deployment, implantation, installation, or operation, or any malfunction of the investigational medical device.

Note: This definition includes any event resulting from use error or from intentional misuse of the investigational medical device.

Note: This includes “comparator” if the comparator is a medical device.

10.1.4 Serious Adverse Device Effect (SADE)

Adverse device effect that has resulted in any of the consequences characteristic of a serious adverse event.

10.1.5 Unanticipated Serious Adverse Device Effect (USADE)

Serious adverse device effect which by its nature, incidence, severity or outcome has not been identified in the current risk assessment.

Note: Anticipated serious adverse device effect (ASADE) is an effect which by its nature, incidence, severity or outcome has been identified in the risk assessment.

10.2 Adverse Event Device and Procedure Relatedness

Based on clinical judgment, the Investigator must provide a determination of device and procedure relationship for adverse events according to the following categories:

- Causal Relationship (Definite) – The adverse event is clearly related to the study device: the event has a temporal relationship to the study device, follows a known pattern of response, or is otherwise logically related to the study device, and no alternative cause is present.
- Probable – The adverse event is likely related to the study device: the event has a temporal relationship to the study device, follows a known or suspected pattern of response, or is otherwise logically related to the study device, but an alternative cause may be present.
- Possible – The adverse event is unlikely related to the study device: the event does not follow a clear temporal relationship to the study device or does not follow a known pattern of response, or is otherwise possibly to be due to the subject's clinical state or other modes of therapy.

In some cases, the adverse event may not be adequately assessed because information is insufficient or contradictory and/or the data cannot be verified or supplemented. Maximum effort will be made to define and categorize the event and avoid these situations. If relatedness remains uncertain, then classify the event as “possible”.

 SHOCKWAVE <small>MEDICAL INC</small>	No.: CP 67398	REV. C
	TITLE: FORWARD PAD IDE Study Protocol	
	CLASS: CLINICAL PROTOCOL	PAGE 40 OF 65

- Not Related – The adverse event is clearly not related to the study device: the event has no temporal or other relationship to the administration of the investigational device, follows no known or suspected pattern of response, and an alternative cause is present.

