7.9.1 When and How to Withdraw Subjects

Subjects may be withdrawn with the medical discretion of the physician, or they may voluntarily withdraw their consent at any time without impact to their medical treatment. When a subject is withdrawn, all data obtained prior to the time of withdrawal may be submitted to the Study Sponsor and be included in the study database, unless otherwise requested by the subject in writing.

 SHOCKWAVE MEDICAL INC.	No.: CP 67398	REV. C
	TITLE: FORWARD PAD IDE Study Protocol	
	CLASS: CLINICAL PROTOCOL	PAGE 32 OF 65

In the event a subject is lost to follow-up or cannot be contacted for post-treatment assessments, at least three attempts (two phone calls and a certified letter) will be made to locate the study subject, and these efforts will be documented. If the subject cannot be located, the subject's lost to follow-up status will be documented in the EDC and they will be exited from the study.

Should the subject expire, adverse event and study exit/withdrawal forms should be completed. Physician assessment is required to determine if the cause of death was possibly or definitely related to the JAVELIN Peripheral IVL Catheter. If available, copies of the death certificate and/or an autopsy report should be included in the research records. The Investigator may need to provide written notification to the IRB upon the death of the study subject, dependent on the IRB policies. Associated regulatory bodies may also be required to be notified depending on local jurisdiction and relatedness to the study device and procedures.

 SHOCKWAVE <small>MEDICAL INC</small>	No.: CP 67398	REV. C
	TITLE: FORWARD PAD IDE Study Protocol	
	CLASS: CLINICAL PROTOCOL	PAGE 33 OF 65

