13.0 STUDY COMMITTEES

13.1 Clinical Events Committee (CEC)

To meet the ethical responsibilities and standards for research subjects, an independent Clinical Events Committee shall serve as forum for adjudication of certain pre-specified clinical event types, including SAEs, as described in the CEC charter.

The CEC will be managed [REDACTED]

In order to enhance objectivity and reduce the potential for bias, the CEC shall be independent of the Study Sponsor as well as the study investigators.

The CEC is made up of clinicians with pertinent expertise who are not participants in the study and who do not have any other real or potential conflicts of interest. Members have expertise in peripheral endovascular procedures, are experienced in the conduct of controlled clinical trials and have knowledge of bioethics and integrity related to the duties and responsibilities to be performed.

The CEC is charged with the development of specific criteria used for the categorization of adverse events and clinical endpoints in the study. Criteria will be established for selected complications and clinical events. Events to be adjudicated include death, MAEs, revascularizations, and amputations. The CEC will also adjudicate relationship to the study device and study procedure according to the following classifications: definitely related, probably related, possibly related, unlikely related and not related.

At the onset of the study, the CEC will establish explicit rules outlining the minimum amount of data required and the algorithm followed in order to classify an event. The methodology for performing these responsibilities shall be developed and outlined in the CEC Charter. Operational provisions shall be established to minimize potential bias (i.e., CEC members shall be blinded to the clinical site to the extent possible during adverse event review and adjudication). The methodology for performing these responsibilities shall be developed and outlined in the CEC Charter. In addition, the CEC Charter will include the number of members, responsibilities, CEC meeting procedures, and meeting frequency.

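### The investigator category *Possible* is defined as unlikely related and is also the default for uncertain events, which leaves ADE, SADE and USADE classification ambiguous

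*Protocol*

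**What the plan says.** Protocol 10.2 asks the investigator to rate device and procedure relationship on four levels: *Definite*, *Probable*, *Possible* and *Not Related*. The last three open as follows:

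- "Probable – The adverse event is likely related to the study device"
- "Possible – The adverse event is unlikely related to the study device"
- "Not Related – The adverse event is clearly not related to the study device"

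For events with insufficient or contradictory information, 10.2 adds: "If relatedness remains uncertain, then classify the event as" *possible*.

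Protocol 13.1 has the CEC rate relationship to the device and to the procedure on a different scale: "definitely related, probably related, possibly related, unlikely related and not related".

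The device-effect definitions depend on this judgement. Protocol 10.1.3 defines an ADE as: "Adverse event related to the use of an investigational device". A SADE (10.1.4) is an ADE with a serious consequence, and a USADE (10.1.5) is a SADE not identified in the risk assessment. Under 10.4.4 the sponsor finds SADEs by screening ADEs. Under 10.4.5 the investigator submits USADEs.

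For deaths, Protocol 7.9.1 asks the physician to "determine if the cause of death was possibly or definitely related to the JAVELIN Peripheral IVL Catheter".

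The SAP contains no relatedness rule.

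**The concern.** A *possible* level normally means that a device cause cannot be excluded. Here the label says that and the definition says the opposite, while the default rule adds events that nobody could assess. Once an event carries this code, the site data do not show which of the three was meant.

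ADE, SADE and USADE status all turn on whether an event is related, and the documents do not say on which side *Possible* falls. Two sites could apply the text in good faith and classify the same event differently. In a single-arm study, device attribution comes from such judgements and not from a comparison with a control group, so the code should have one meaning. Procedure relatedness has a further gap: 10.2 requires it, but all four definitions mention only the study device.

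**Working it through.** No arithmetic applies, because the documents give no event counts and no figure rests on relatedness. The check sets the two scales side by side and follows each kind of event through the definitions.

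**Step 1. Compare the scales.**

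| Judgement about the event | Site code (10.2, four levels) | CEC level (13.1, five levels) |
|---|---|---|
| Clear causal link | *Definite* | definitely |
| Likely | *Probable* | probably |
| Genuinely possible, neither likely nor unlikely | no level of its own; only *Possible* is available | possibly |
| Unlikely | *Possible*, by definition | unlikely |
| Cannot be assessed | *Possible*, by default | not stated in the protocol |
| Clearly not related | *Not Related* | not related |

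Three rows fall under one site code, and that code corresponds to at least two CEC levels. No mapping is given.

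**Step 2. See how wide the code is.** *Not Related* requires three things together: no temporal or other relationship, no known or suspected pattern, and an alternative cause. An event that fails any of these and is not likely related has nowhere to go except *Possible*.

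**Step 3. Try both readings of related.**

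- If *Possible* counts as related, events judged unlikely enter the ADE, SADE and USADE counts.
- If *Possible* does not count as related, events that are genuinely possible, and those that could not be assessed, drop out.

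No cut-off on the four-level scale separates these groups.

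**Step 4. Look for a rule elsewhere.**

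- 10.1.3 to 10.1.5 use relatedness without naming levels.
- 12.0 makes the sponsor responsible for classifying adverse events but gives no rule.
- 13.1 does not say that the CEC rating replaces the site rating.
- 7.9.1 puts *possibly* beside *definitely*, which sits badly with a *Possible* that means unlikely, and it leaves out *probably*.

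**Step 5. See what the ambiguity reaches.**

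- *Serious events.* Under 10.4.2 and Table 3, every SAE is due at the sponsor within 2 business days whatever its relatedness. SADEs and USADEs have the same limit.
- *Non-serious events.* Table 3 treats AEs and ADEs alike for timing. 10.4.2 and 13.1 describe CEC review of SAEs, deaths, MAEs, revascularizations and amputations. No CEC review of non-serious ADEs is stated, so no second rating is provided for.
- *Endpoints.* The MAE components in Protocol 5.1 and SAP 4.1 do not use device relatedness, and neither do the effectiveness or secondary endpoints. Sample size and power are untouched.

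**The case against.** The strongest reply is that this is close to a one-word slip in a text that leans toward inclusion. *Not Related* is narrow, uncertain events are placed above it, and 7.9.1 groups *possibly* with *definitely* for deaths. The rest of the *Possible* definition, which speaks of an unclear temporal relationship or a possible other cause, would suit an ordinary *possible*. Several layers also stand behind the site label: the 2-day SAE rule, sponsor classification (12.0), the CEC's own five-level rating, DSM evaluation of all adverse events (13.2) and separate reporting of device deficiencies (10.3.2). The CEC charter and case report forms are not among the documents and may contain a mapping.

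Much of this stands. A reader might infer that uncertain serious events will miss the USADE route, or that the counts are wrong in a known direction. The documents support neither. Serious events reach the sponsor and the CEC whatever the site code, and counting *Possible* as related would err only toward over-inclusion. Nor does the SAP plan a relatedness table or a site-versus-CEC comparison that would be spoiled.

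What does not stand is that the safeguards settle the classification. An inclusive lean is not a stated rule, the sponsor and CEC are not told which rating governs, and the CEC layer is not stated to cover non-serious ADEs. The side points are minor: the wording in 7.9.1 can be read as the ends of a range, and the lead-in to 10.2 does apply the scale to the procedure as well.

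**Conclusion.** The point holds as an internal contradiction with a limited reach. Protocol 10.2 puts unlikely, genuinely possible and unassessable events under one site code. Protocol 13.1 separates *possibly* from *unlikely*, and neither document says which site levels count as related or whose rating decides. ADE, SADE and USADE classification and counts are therefore ambiguous. The effect falls mainly on non-serious ADEs and on any relatedness reported in safety summaries.

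Its size cannot be given, because the documents contain no event counts and no expected share of *Possible* ratings. The conclusion assumes that the unseen CEC charter and case report forms do not already resolve the matter. It does not touch SAE timing, the primary or secondary endpoints, sample size or power. It should be corrected before relatedness is tabulated, but it does not threaten the primary analysis.

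**What to change.** 1. In Protocol 10.2, define *Possible* as a relationship that cannot be ruled out. Move the present wording to a separate *Unlikely* level, so that the site scale has the same five levels as 13.1.
2. State that *Definite*, *Probable* and *Possible* count as related for ADE, SADE and USADE.
3. State whether the site or the CEC rating is tabulated, and which rating applies to non-serious events that the CEC does not review.
4. Word each level for both study device and study procedure.
5. Use the same terms for deaths in 7.9.1.

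The cost is a small protocol edit, a change to the adverse event form and a short notice to sites. Events already coded *Possible* under the present wording would need re-rating. That extends to Mini S only if it uses the same scale. Protocol 9.1 and SAP 7 say that the two studies share data collection requirements, but the Mini S relatedness scale is not in these documents and should be checked first.
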